7.3.4. Period 5 (Study Assessment Day 25 through Study Assessment Day 31)

Documentation of receipt of PRBC transfusion(s) will be provided on an eCRF. If the study subject has NOT received \geq 10 PRBC transfusions (see Section 9.3.1), proceed with required assessments.

Required assessments [following confirmation that subject is still receiving ganciclovir (e.g., that the ganciclovir has not been permanently discontinued)]: 1) virology blood specimens for CMV viral load (required amount of whole blood for CMV PCR is 0.5 mL); 2) CMV detection from noninvasive urine specimen (if obtainable); 3) ganciclovir dosing information (mg/dose, dosing interval, subject weight).

Optional assessments (if being drawn for clinical reasons; any laboratory value obtained during the window will suffice, with an effort being made to capture the most abnormal value): 1) hematology labs (WBC with differential, hemoglobin, platelet count); 2) chemistry labs (AST, ALT); 3) serum creatinine.

Study Assessments (as described)	Optional Assessments*
Virology blood specimens for CMV viral load	Hematology labs (WBC with differential, hemoglobin, platelet count)
If obtainable, CMV detection from noninvasive urine specimen (e.g., bagged, from indwelling foley catheter, excess clinical specimen, etc.)	Chemistry labs (AST, ALT)
Ganciclovir dosing information (mg/dose, dosing interval, subject weight)	Serum creatinine

* If being drawn for clinical reasons; any laboratory value obtained during the window will suffice, with an effort being made to capture the most abnormal value

7.3.5. Period 6 (Study Assessment Day 32 through Study Assessment Day 38)

Documentation of receipt of PRBC transfusion(s) will be provided on an eCRF. If the study subject has NOT received ≥ 10 PRBC transfusions (see Section 9.3.1), proceed with required assessments.

Required assessments [following confirmation that subject is still receiving ganciclovir (e.g., that the ganciclovir has not been permanently discontinued)]: 1) virology blood specimens for CMV viral load (required amount of whole blood for CMV PCR is 0.5 mL); 2) CMV detection from noninvasive urine specimen (if obtainable); 3) ganciclovir dosing information (mg/dose, dosing interval, subject weight).

Optional assessments (if being drawn for clinical reasons; any laboratory value obtained during the window will suffice, with an effort being made to capture the most abnormal value): 1) hematology labs (WBC with differential, hemoglobin, platelet count); 2) chemistry labs (AST, ALT); 3) serum creatinine.

Study Assessments (as described)	Optional Assessments*
Virology blood specimens for CMV viral load (NOTE: if subject weighs < 600 grams, this virology specimen will not be obtained)	Hematology labs (WBC with differential, hemoglobin, platelet count)
If obtainable, CMV detection from noninvasive urine specimen (e.g., bagged, from indwelling foley catheter, excess clinical specimen, etc.)	Chemistry labs (AST, ALT)
Ganciclovir dosing information (mg/dose, dosing interval, subject weight)	Serum creatinine

* If being drawn for clinical reasons; any laboratory value obtained during the window will suffice, with an effort being made to capture the most abnormal value

7.4 Final Study Visit

7.4.1. Period 7 (Study Assessment Day 39 through Study Assessment Day 42)

Documentation of receipt of PRBC transfusion(s) will be provided on an eCRF. If the study subject has NOT received ≥ 10 PRBC transfusions (see Section 9.3.1), proceed with required assessments.

Required assessments [following confirmation that subject is still receiving ganciclovir (e.g., that the ganciclovir has not been permanently discontinued)]: 1) virology blood specimens for CMV viral load (required amount of whole blood for CMV PCR is 0.5 mL); 2) CMV detection from noninvasive urine specimen (if obtainable); 3) ganciclovir dosing information (mg/dose, dosing interval, subject weight).

Optional assessments (if being drawn for clinical reasons; any laboratory value obtained during the window will suffice, with an effort being made to capture the most abnormal value): 1) hematology labs (WBC with differential, hemoglobin, platelet count); 2) chemistry labs (AST, ALT); 3) Serum creatinine.

Study Assessments (as described)	Optional Assessments*
Virology blood specimens for CMV viral load (NOTE: if subject weighs < 650 grams, this virology specimen will not be obtained)	Hematology labs (WBC with differential, hemoglobin, platelet count)
If obtainable, CMV detection from noninvasive urine specimen (e.g., bagged, from indwelling foley catheter, excess clinical specimen, etc.)	Chemistry labs (AST, ALT)
Ganciclovir dosing information (mg/dose, dosing interval, subject weight)	Serum creatinine

* If being drawn for clinical reasons; any laboratory value obtained during the window will suffice, with an effort being made to capture the most abnormal value

7.5 Early Termination Visit

Study subjects may withdraw voluntarily from participation in the study at any time. If a study subject withdraws or is discontinued from the study at any time prior to completion of the study, the reason for this decision will be recorded on the eCRFs. The remaining follow-up evaluations will be conducted if patient consent is obtained. SAEs and AEs will be followed according to guidelines in Section 9.

Should a study subject's therapy be discontinued prematurely, all clinical and laboratory evaluations scheduled during the next study visit will be completed on the day the study subject is discontinued. All key endpoints will be evaluated and all randomized study subjects will continue to be followed as long as possible and included in the final analysis.

7.6 Unscheduled Visit

All subjects enrolled on the study are hospitalized. As such, there will not be unscheduled visits.

8 STUDY PROCEDURES/EVALUATIONS

The study procedures and evaluations are summarized in Appendix A. In the conduct of this study, hospital staff may perform research activities (e.g., pharmacokinetic blood draw collection, serum creatinine collection, blood CMV viral load collection, urine collection for CMV), under the direction of the site Principal Investigator or designee.

8.1 Clinical Evaluations

8.1.1. Baseline Demographics

To characterize the study subjects, information will be recorded at the baseline study visit (Period 1) following the obtaining of informed consent. Data collected will include basic demographics and birth history (date of birth; gender; race; ethnicity; birth weight; weight at enrollment; length in centimeters at enrollment; reason ganciclovir is being administered, gestational age at birth; ganciclovir dose and dosing frequency at time of enrollment; detailed ganciclovir dose and dosing frequency since ganciclovir therapy was initiated; manufacturer of the ganciclovir lot utilized at the treating facility; and date ganciclovir therapy was initiated).

8.2 Laboratory Evaluations

Chemistry labs (serum creatinine) will be drawn on the calendar day that ganciclovir PKs are being drawn; required amount of whole blood for serum creatinine is 0.25 mL. All other chemistry labs (serum creatinine, AST, and ALT) and hematology labs (WBC with differential, hemoglobin, platelet count) will be recorded on eCRFs if they have been drawn for clinical reasons; any laboratory value obtained during the window will suffice, with an effort being made to capture the most abnormal value.

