2.3 Potential Risks and Benefits

2.3.1 Potential Risks

As a sampling study, the potential risks relate to blood draws (e.g., bruising at the site, infection, anemia possibly requiring packed red blood cell transfusion). Requiring a baby to be at least 500 grams at the time of study enrollment will ensure that blood volumes withdrawn will be acceptable by research standards. Additionally, virtually all of the subjects will have long-term intravenous access for clinical care, through which blood can be withdrawn without risk of discomfort from the needle stick or bruising at the site during or after the blood drawing and rarely an infection. Transfusions are expected in hospitalized premature infants. One study reported that extremely premature neonates receive an average of 5.2 ± 4.2 transfusions over a six week period.³¹ Other trials have reported similar numbers of transfusions in this population.^{32,33} It is possible that even higher numbers of transfusions might be experienced in the at-risk population in this sampling study since they are receiving the myelosuppressive drug ganciclovir as part of clinical care. Transfusions are not associated with long-term sequelae.³³ Nevertheless, throughout the conduct of this study, transfusion rates will be carefully monitored.

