Both whole blood for CMV PCR and urine for CMV assessment will be obtained serially through Study Assessment Period 7 as long as the subject is receiving intravenous ganciclovir therapy (that is, until the ganciclovir is permanently discontinued). These specimens will be used to determine viral load and, as indicated, ganciclovir resistance. At each sample collection time, urine will be split into two aliquots. These aliquots will be available for CMV detection as appropriate, based upon whole blood viral loads. Specimens will then be available for subsequent testing for ganciclovir resistance in the UAB Virology Resistance Laboratory. Since ganciclovir is a renally excreted drug, serum creatinine will be drawn for the research protocol on the day that the ganciclovir pharmacokinetic specimens are obtained in order to calculate creatinine clearance using a method such as the modified Schwartz formula, and thus correlate ganciclovir clearance with renal function. Otherwise, data from hematology assessments (WBC count and differential, hemoglobin, platelet count) and from chemistry labs (serum creatinine, ALT, and AST) will be recorded on the study case report forms each study assessment period if they are being obtained for clinical reasons, but will not be drawn only for the purposes of the study. Ganciclovir dosing information (mg/dose, dosing interval, and subject weight) will be recorded on the day of the pharmacokinetic blood draws. Once a subject is successfully enrolled into the study the ganciclovir dosing information (mg/dose and dosing interval) will be recorded from the start of clinical treatment of ganciclovir until date of enrollment. After enrollment ganciclovir dosing information (mg/dose and dosing interval) will be captured from Study Assessment Period 1 through the Study Assessment Period 7; as long as the subject is receiving intravenous ganciclovir therapy.

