7.2 Enrollment/Baseline

7.2.1. Baseline Assessment (Period 1: Study Assessment Day 1 through Study Assessment Day 3, unless broader window specified)

- Confirm that informed consent has been obtained from parent or legally authorized representative
- Document baseline demographics (see Section 8.1.1; Window: Birth through Study Assessment Day 3)
 - Gestational age at delivery
 - Date of birth
 - Day of life at initiation of IV ganciclovir therapy
 - Gender
 - Race
 - Ethnicity
 - Birth weight
 - Weight at enrollment
 - Length in centimeters at enrollment
 - Reason ganciclovir being administered
 - Ganciclovir dose and dosing frequency
 - Manufacturer of the ganciclovir lot utilized at the treating facility
 - Date ganciclovir therapy was initiated
- Hematology labs (see Section 8.2; Window: Birth through Study Assessment Day 3)
 - WBC with differential, hemoglobin, and platelet count, if being drawn for clinical reasons; any laboratory value obtained during the window will suffice, with an effort being made to capture the most abnormal value
- Chemistry labs (see Section 8.2; Window: Birth through Study Assessment Day 3)
 - AST and ALT, if being drawn for clinical reasons; any laboratory value obtained during the window will suffice, with an effort being made to capture the most abnormal value

- Serum Creatinine (see Section 8.2.)
 - To be drawn on the calendar day that ganciclovir PKs are being drawn (Window: Study Assessment Day 1 through Study Assessment Day 5)
 - Required amount of whole blood for serum creatinine is 0.25 mL
- Ganciclovir pharmacokinetics (see Section 8.2.2.2.)
 - Ganciclovir concentrations will be obtained with one of the Study Assessment Dose 3, 4, 5, 6, 7, or 8 (Window: Study Assessment Day 1 through Study Assessment Day 5)
 - Timepoints for pharmacokinetic draws: 0h (immediately prior to IV ganciclovir dose; window: -15 min), 1h (immediately after the end of the IV ganciclovir dose; window: +15 min), 2-3h, 5-7h, and 10-12h
 - Required amount of whole blood for plasma ganciclovir determination at each timepoint is 200 μ L (0.2 mL)
- Virology specimens (see Sections 8.2.2.1.)
 - Blood for CMV quantitative PCR will be obtained (required amount of whole blood for CMV PCR is 0.5 mL)
 - If obtainable, urine for CMV detection will be collected non-invasively (e.g., bagged, from indwelling foley catheter, excess clinical specimen, etc.)
- Clinical treatment ganciclovir dosing information
 - mg/dose
 - Dosing interval
 - Patient weight

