h) Ganciclovir concentrations will be obtained with one of the Study Assessment Doses 3, 4, 5, 6, 7, or 8 (Window: Study Assessment Day 1 through Study Assessment Day 5) at the following time points: 0h (immediately prior to IV ganciclovir dose; window: -15 min), 1h (immediately after the end of the IV ganciclovir dose; window: +15 min), 2-3h, 5-7h, and 10-12h; required amount of whole blood for plasma ganciclovir determination at each time point is 200 μ L (0.2 mL). Study related laboratory draws will be delayed or deferred if the investigator believes that obtaining them might increase subject risk. Additionally, a study-related laboratory specimen that is unevaluable due to clotting or laboratory related issues will not be repeated. If a study related laboratory draw is delayed or deferred, study staff will document this on a source document.

i) If desired by the treating physicians, ganciclovir concentrations may be obtained around one dose during the window at the following time points: 0h (immediately prior to IV ganciclovir dose; window: -15 min), 1h (immediately after the end of the IV ganciclovir dose; window: +15 min), 2-3h, 5-7h, and 10-12h; required amount of whole blood for plasma ganciclovir determination at each time point is 200 μ L (0.2 mL). Optional laboratory draws are not required by the protocol, and so no documentation on a source document will be required.

j) If subject weighs < 575 grams, the second set of PK draws cannot be performed (would exceed blood draw parameters of 7 mL/kg over 42 days)

k) To be obtained only once per study period; ideally, at least 72 hours should separate viral loads being obtained in different study periods

l) Required amount of whole blood for CMV PCR is 0.5 mL. Study related laboratory draws will be delayed or deferred if the investigator believes that obtaining them might increase subject risk. Additionally, a study-related laboratory specimen that is unevaluable due to clotting or laboratory related issues will not be repeated. If a study related laboratory draw is delayed or deferred, study staff will document this on a source document.

m) If subject weighs < 600 grams, the virology specimen for CMV viral load will not be performed (would exceed blood draw parameters of 7 mL/kg over 42 days)

n) If subject weighs < 650 grams, the virology specimen for CMV viral load will not be performed (would exceed blood draw parameters of 7 mL/kg over 42 days)

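### The PK-day research creatinine (0.25 mL) is required with no provision for a clinical creatinine already drawn that calendar day to serve instead

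*Protocol*

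**What the plan says.** Section 4 of the protocol, like the Protocol Summary, states that "serum creatinine will be drawn for the research protocol on the day that the ganciclovir pharmacokinetic specimens are obtained", so that creatinine clearance can be calculated and related to ganciclovir clearance. Section 7.2.1 adds the volume: "Required amount of whole blood for serum creatinine is 0.25 mL". Section 8.2 has the same rule, "Chemistry labs (serum creatinine) will be drawn on the calendar day that ganciclovir PKs are being drawn; required amount of whole blood", and gives the same volume. It then treats the remaining labs differently: "All other chemistry labs (serum creatinine, AST, and ALT) and hematology labs (WBC with differential, hemoglobin, platelet count) will be recorded on eCRFs if". The condition there is that the sample was taken for clinical care, and any value in the window is accepted. Appendix A footnote g ties the creatinine to the calendar day of the PK draws, and the SAP repeats it under Table 1 of its CRF Workflow section. Section 7.3.3 asks for a creatinine on the PK day in Period 4 if the optional second PK set is taken.

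On blood volume, section 2.3.1 gives this assurance: "Requiring a baby to be at least 500 grams at the time of study enrollment will ensure that blood volumes withdrawn will be acceptable". Appendix A footnotes j, m and n justify the 575, 600 and 650 g cut-offs because a draw below them "would exceed blood draw parameters of 7 mL/kg over 42 days".

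**The concern.** The creatinine has one stated purpose and one timing rule, which is the calendar day of the PK profile. A clinical creatinine from that day satisfies both. Section 8.2.1 names only CMV viral load/resistance and pharmacokinetics as central-laboratory research assays, so no central creatinine assay explains a separate sample. Yet clinical values are accepted only for the other labs.

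The protocol treats blood draws as the study's risk, and this draw falls in the period with the largest required study volume. Where a same-day clinical value exists, the research sample adds blood loss and no information that the plan asks for.

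**Working it through.** **Inputs.** PK: five time points at 0.2 mL (Appendix A footnote h: "required amount of whole blood for plasma ganciclovir determination at each time point is 200" µL). Creatinine: 0.25 mL (sections 7.2.1 and 8.2). CMV PCR: 0.5 mL per period, with no weight cut-off in Periods 1 to 5, then 600 g in Period 6 and 650 g in Period 7 (section 8.2.1.1). Second PK set: 575 g or more. Limit: 7 mL/kg over 42 days. Minimum weight at enrollment: 500 g.

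**The plan's own figure.** Period 1 = 5 × 0.2 + 0.25 + 0.5 = 1.75 mL. This matches Appendix A, so the total includes the research creatinine. Without it, Period 1 is 1.50 mL.

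**Size of the redundant draw.**
- Share of Period 1: 0.25 / 1.75 = 14%.
- At 500 g: 0.25 / 0.5 = 0.5 mL/kg, which is 0.5 / 7 = 7% of the limit.

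**The separate question of the limit.** Later periods add 0.5 mL each. With no second PK set, cumulative volume divided by the cut-off weight gives:

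| Through | Weight | With creatinine | Without creatinine | Weight needed for 7 mL/kg, with creatinine |
|---|---|---|---|---|
| Period 5 | 500 g | 3.75 mL = 7.50 mL/kg | 3.50 mL = 7.00 mL/kg | 3.75 / 7 = 536 g |
| Period 6 | 600 g | 4.25 mL = 7.08 mL/kg | 4.00 mL = 6.67 mL/kg | 4.25 / 7 = 607 g |
| Period 7 | 650 g | 4.75 mL = 7.31 mL/kg | 4.50 mL = 6.92 mL/kg | 4.75 / 7 = 679 g |

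At a constant 500 g the running total with creatinine is 3.5, 4.5, 5.5, 6.5 and 7.5 mL/kg over Periods 1 to 5, so the limit is first passed at the Period 5 draw (Days 25 to 31).

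Second PK set, through Period 4 at 575 g:
- No creatinine: 4 × 0.5 + 2 × 1.0 = 4.00 mL, or 6.96 mL/kg.
- With the Period 1 creatinine: 4.25 mL, or 7.39 mL/kg.
- With a Period 4 creatinine as well: 4.50 mL, or 7.83 mL/kg.

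At each of these cut-offs the total is at or under 7 mL/kg only if creatinine is left out.

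**Period 4 side by side.** Section 7.3.3 calls for a creatinine on the day of the second PK set. In Appendix A the Period 4 creatinine carries only footnote e (recorded if drawn for clinical reasons), and the total with PK is 1.5 mL = 1.0 + 0.5, which leaves no room for a research creatinine. With 0.25 mL added it would be 1.75 mL.

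**The case against.** The strongest reply is that the documents never address the case. No passage orders a second sample when one was taken that day or forbids using the clinical result. The phrase about drawing for the research protocol can be read as making sure that a value exists, and the Manual of Procedures, which might settle it, is not among the documents. This stands as far as consequences go. A reader might infer that a site using the clinical value commits a deviation, since section 15.6 defines deviations broadly. The documents do not say so, and the point should not rest on it. What remains is that the requirement is unconditional, the volume is budgeted, and the rule accepting clinical values is confined to the other labs.

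Nor is it true that a clinical creatinine is nowhere accepted on a PK day. The Period 4 entry in Appendix A treats it that way, though in conflict with section 7.3.3.

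Section 5.3.2 and footnote g provide for delaying or deferring draws that the investigator believes might increase risk. That mitigates, but it depends on the investigator's judgment, is not tied to 7 mL/kg, and does not let a clinical value stand in. Deferral could lose the PK-day creatinine, whereas substitution keeps it.

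Finally, a clinical sample may be some hours from the PK dose. That is true, but the plan itself asks for no closer match than the calendar day.

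**Conclusion.** The point holds as a cheap improvement. As written, an infant with a same-day clinical creatinine gives 0.25 mL for no added information (0.5 mL/kg at 500 g). The total benefit cannot be quantified, because the share of such infants is not given.

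A reader might go further and infer that the redundant creatinine is what breaks the 7 mL/kg limit, and that substitution would cure this. The documents do not support that:
- The excess comes from cut-offs that fit the limit only without creatinine, and from having no cut-off at Period 5. Infants without a same-day clinical value would still reach 7.5, 7.08 or 7.31 mL/kg at those weights.
- At 500 g the schedule without creatinine is exactly 7.0 mL/kg, so there is no margin. The SAP copy gives the PK and PCR volumes as minimums.
- The Period 5 excess needs an infant still on ganciclovir at Days 25 to 31 and still under 536 g. Section 2.1 puts treatment generally at two to four weeks, and study draws end when ganciclovir is permanently stopped. Growth may also remove the excess, but the protocol gives no growth figures.

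The excess at the cut-off weights and the Period 4 conflict are real inconsistencies, but separate ones.

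**What to change.** In the Protocol Summary, sections 4, 7.2.1, 7.3.3 and 8.2, Appendix A footnote g and the SAP copy, state that a clinical serum creatinine drawn on the same calendar day as the PK profile is used if there is one. The 0.25 mL research sample is drawn only if there is none, and the source is recorded. Show the Period 1 volume as 1.5 or 1.75 mL.

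The cost is wording, one data field for the source, and IRB approval of the amendment. The only downside is the possible gap of some hours between the clinical sample and the PK dose.

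Separately, reconcile the stated volumes, the weight cut-offs, the 500 g assurance in section 2.3.1 and the 7 mL/kg limit with creatinine counted. Reconcile the Period 4 creatinine entry and 1.5 mL total in Appendix A with section 7.3.3. Which of these should change is for the sponsor to decide.

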8.2.1 Special Assays or Procedures

Research assays (CMV viral load/resistance and pharmacokinetics will be conducted at the respective UAB Central labs).

8.2.1.1. CMV Viral Load/Resistance Testing

[figure not shown]
Assessment of CMV viral load in whole blood will be conducted at the UAB Central Laboratory. The required amount of whole blood for CMV PCR is 0.5 mL. Whole blood will be collected at each study visit from Period 1 through Period 5. Whole blood will also be collected at the Period 6 study visit if the

subject weighs at least 600 grams, and at the Period 7 study visit if the subject weighs at least 650 grams.

Urine collection by noninvasive mechanism (e.g., bagged, indwelling foley catheter, excess clinical specimen, etc.) will be attempted at each study visit. If urine is obtainable, it will be frozen and sent to the UAB Central Laboratory for processing. If an attempt to obtain urine for CMV detection is unsuccessful, study staff will document the failed attempt on a source document. All specimens collected will be sent to the UAB Central Laboratory.

Viral detection assays will be performed in the UAB Central Laboratory. These assays and tests are in clinical and research use already in the Central Laboratory. The detection of CMV DNA will be performed using the CMV two primer Taqman assay already employed regularly in our laboratory. The detection limit of our real-time PCR assay, as determined by the sensitivity titration analysis, is 10 genomic equivalents per reaction. The results of 10 different runs on different days are shown in the Table below. Regression analysis shows a very high correlation coefficient (0.9996) for the 6 log concentration range (see Figure below).

genome equivalents	log(10)	# +/10	ct(mean)	std
1000000	6	10/10	18.362	0.085609
100000	5	10/10	21.476	0.155863
10000	4	10/10	24.855	0.187157
1000	3	10/10	28.321	0.305449
100	2	10/10	31.869	0.2283
10	1	10/10	35.283	0.606045

The amplification efficiency is calculated to be 1.95 with the theoretical maximum of 2.0, which would indicate a doubling with each PCR cycle. Each assay contains a No Target Control and inhibition is monitored using a house-keeping gene, human albumin. This 2 primer set assay has been used for several previous studies and has been utilized in the Children's Diagnostic Virology Laboratory for 2 years, primarily to monitor transplant patients. The Diagnostic Laboratory participates in the College of American Pathologists, CAP, quantitative unknowns for CMV, EBV and BK viruses. Over the last 3 cycles, the CMV assay has been within 4 fold of the mean for these unknowns and has improved with each group.

Antiviral resistance will be performed in the UAB Viral Resistance Laboratory. Lab testing of viral isolates for ganciclovir resistance will be conducted by a standing SOP with a fully characterized assay.

